
Pembrolizumab is a potent and highly selective humanized monoclonal antibody (mAb) of the

IgG4/kappa isotype designed to directly block the interaction between PD-1 and its ligands, PD-L1 and PD-L2. Keytruda™ (pembrolizumab) has recently been approved in the United States for the treatment of patients with non-small cell lung cancer or those with unresectable or metastatic melanoma and disease progression following ipilimumab and, if BRAF V600 mutation positive, a BRAF inhibitor.

PD-1 inhibitors including pembrolizumab have promising activity in solid tumors although their activity in acute leukemia is unknown. A Phase Ib/II study of pembrolizumab in relapsed/refractory hematologic malignancies is ongoing. PD-L1, but not PD-L2, is expressed in a subset of ALL primary cells and in most lymphoid leukemia/lymphoma cell lines [11,12]. PD-L1 also tends to be upregulated in the setting of relapsed malignancies including ALL [13,14]. IFN-gamma and TNF-alpha cause upregulation of PD-L1 in acute leukemia [15] which may potentially contribute to resistance to the effects of blinatumomab given the high expression of IFN-gamma, TNF-alpha and other inflammatory cytokines with blinatumomab treatment. Taken together, pembrolizumab holds promise to augment the effect of blinatumomab in patients with relapsed or refractory B-lineage ALL.

Pembrolizumab is generally well tolerated as monotherapy with principal adverse events being rare immune checkpoint blockade-related toxicities. Adverse events in 411 melanoma patients included pneumonitis in 2.9% (0.2% Grade 3), immune-mediated colitis in 1% (0.5% Grade 3), hepatitis in 0.5% (0.2% Grade 4), hypophysitis in 0.5% (0.2% Grade 4), hyperthyroidism in 1.2% (0.2% Grade 3), hypothyroidism in 8.3% (0.2 % Grade 3), type I diabetes mellitus, and immune-mediated nephritis in 0.7% (0.5% Grade 3 or 4). Treatment with prednisone 40 mg or greater per day led to resolution of symptoms in the large majority of patients. Infusion reactions are rare with pembrolizumab but may occur. The effect of pembrolizumab on the developing fetus is unknown.

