5.7 Toxicities and Dosing Delays/Dose Modifications

Any patient who receives treatment on this protocol will be evaluable for toxicity. Each patient

will be assessed for the development of toxicity except cytokine release syndrome (see below, grading/management per Lee et al. Blood 2014) according to the NCI Common Toxicity Criteria for Adverse Events (CTCAE), version 4.03. Dose adjustments should be made according to the system showing the greatest degree of toxicity. As Blinatumomab is an approved treatment for this indication, reducing or withholding pembrolizumab should be considered as the first option in response to a toxicity prior to adjusting the Blinatumomab dosing.

Adverse events (both non-serious and serious) associated with pembrolizumab exposure may represent an immunologic etiology. These adverse events may occur shortly after the first dose or several months after the last dose of treatment. Pembrolizumab and blinatumomab must be withheld for drug-related toxicities and severe or life-threatening AEs as per Tables below. See Section 5.6.1 in Events of Clinical Interest Guidance Document for additional supportive care guidelines.

All dose adjustments presume that the toxicity is determined by the investigator to be possibly, probably, or definitely related to blinatumomab, pembrolizumab, or both. Withholding the dose and dose adjustments should not occur if toxicity is felt unlikely to be or definitely not related to study blinatumomab, pembrolizumab, or both.

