5.7.1 Management of non-Hematologic Toxicities

As Blinatumomab is an approved treatment for this indication, reducing or withholding pembrolizumab should be considered as the first option in response to a toxicity prior to adjusting the Blinatumomab dosing.

Any Grade 3 or severe AE that recurs should lead to permanent discontinuation of pembrolizumab, as should any persistent grade 2 or 3 AE (excluding endocrinopathies) that do not recover to grade 1 within 12 weeks of the last dose of pembrolizumab.

Cytokine Release Syndrome	Management for Blinatumomab	Management for Pembrolizumab
Grade 1 -Fever -Constitutional symptoms	Continue infusion. Vigilant supportive care. Assess for infection.	No change in dose. Patient should be admitted for subsequent pembrolizumab dose given in combination with blinatumomab and monitored for at least 72 hours after pembrolizumab administration.
Grade 2 -Hypotension responsive to fluids or one low dose pressor** -Hypoxia: reponds to <40% O ₂ -Organ toxicity: Grade 2	Continue infusion. Vigilant supportive care. Assess for infection.	No change in dose. Patient should be admitted for subsequent pembrolizumab dose given in combination with blinatumomab and monitored for at least 72 hours after pembrolizumab administration.
Grade 3 -Hypotension requiring multiple pressors or high dose pressors** -Hypoxia requiring ≥40% O ₂	Withhold* until resolved then resume blinatumomab at 9 mcg/day. Escalate to 28 mcg/day after 7 days if the toxicity does not recur.	Stop Infusion. Additional appropriate medical therapy may include but is not limited to: IV fluids

Cytokine Release Syndrome	Management for Blinatumomab	Management for Pembrolizumab
-Organ toxicity: Grade 3 or Grade 4 transaminitis	Vigilant supportive care. Assess for infection. Consider administration of corticosteroids and/or tocilizumab.	Antihistamines NSAIDS Acetaminophen Narcotics Oxygen Vasopressors Corticosteroids Tocilizumab Increase monitoring of vital signs as medically indicated until the subject is deemed medically stable in the opinion of the investigator. Hospitalization may be indicated. Subject is permanently discontinued from further trial treatment administration.

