Grade 4	Permanently discontinue blinatumomab.	Withhold of permanently discontinue pembrolizumab Treat with non-selective beta-blockers (eg. Propranolol) and/or thionamides as appropriate Monitor for signs and symptoms of the disorders
*Patients requiring a delay of blinatumomab > 14 days due to toxicity should go off protocol therapy.		

Immune-mediated hypothyroidism	Management for Blinatumomab	Management for Pembrolizumab
≤ Grade 1	No change in dose	No change in dose
Grade 2	No change in dose	No Change in dose Initiate thyroid replacement hormones (eg, levothyroxine or liothyronine) per standard of care Monitor for signs and symptoms of thyroid disorders.
Grade 3	Withhold* until resolved to ≤ Grade 1 then resume blinatumomab at 9 mcg/day. Escalate to 28 mcg/day after 7 days if the toxicity does not recur. If immune-mediate hypothyroidism recurs then permanently discontinue blinatumomab.	No change in dose Initiate thyroid replacement hormones (eg, levothyroxine or liothyronine) per standard of care Monitor for signs and symptoms of thyroid disorders.
Grade 4	Permanently discontinue blinatumomab.	No change in dose Initiate thyroid replacement hormones (eg, levothyroxine or liothyronine) per standard of care Monitor for signs and symptoms of thyroid disorders.
*Patients requiring a delay of blinatumomab > 14 days due to toxicity should go off protocol therapy.		

Other Immune-mediated Adverse Reactions	Management for Blinatumomab	Management for Pembrolizumab
≤ Grade 1	No change in dose	No change in dose
Grade 2	No change in dose	Withhold until ≤ Grade 1. Missed doses are not made up. Start prednisone 1-2 mg/kg oral daily with taper over at least 4 weeks after resolution to ≤ Grade 1. If immune-mediated reaction recurs at Grade 2 or higher despite corticosteroids then permanently discontinue pembrolizumab.
Grade 3	Withhold* until resolved to ≤ Grade 1 then resume blinatumomab at 9	Give methylprednisolone 2 mg/kg IV once then prednisone 1-2

Other Immune-mediated Adverse Reactions	Management for Blinatumomab	Management for Pembrolizumab
	mcg/day. Escalate to 28 mcg/day after 7 days if the toxicity does not recur. If immune-mediate reaction recurs then permanently discontinue blinatumomab.	mg/kg oral daily with taper over at least 4 weeks after resolution to ≤ Grade 1. Permanently discontinue pembrolizumab.

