Cytokine release syndrome, hypotension, fever, respiratory distress, encephalopathy, confusion, seizure, infection, tumor lysis syndrome, neutropenia, febrile neutropenia, transaminitis.

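### For Grade 3 and 4 immune-mediated hypothyroidism, the dosing table holds or stops blinatumomab but leaves pembrolizumab unchanged, contrary to the protocol's advisory preference to adjust pembrolizumab first

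*Combined protocol and SAP*

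**What the plan says.** The immune-mediated hypothyroidism table in section 5.7.1 gives these instructions.

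- **Blinatumomab, Grade 3:** withhold until Grade 1 or less, then resume at 9 mcg/day. The cell continues: "Escalate to 28 mcg/day after 7 days if the toxicity does not recur. If immune-mediate hypothyroidism recurs then permanently discontinue blinatumomab".
- **Blinatumomab, Grade 4:** permanent discontinuation.
- **Pembrolizumab, Grades 2, 3 and 4:** the same instruction each time, "No Change in dose Initiate thyroid replacement hormones (eg, levothyroxine or liothyronine) per standard of care".
- **Footnote:** "Patients requiring a delay of blinatumomab > 14 days due to toxicity should go off protocol therapy".

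Section 5.7 and the opening of section 5.7.1 set a general order: "reducing or withholding pembrolizumab should be considered as the first option in response to a toxicity prior to adjusting the Blinatumomab dosing". The reason given is that blinatumomab is already approved for this indication. Section 5.7 also makes the tables binding: "Pembrolizumab and blinatumomab must be withheld for drug-related toxicities and severe or life-threatening AEs as per Tables below". On attribution it says: "All dose adjustments presume that the toxicity is determined by the investigator to be possibly, probably, or definitely related to blinatumomab, pembrolizumab, or both".

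On which drug causes the event, section 1.2.2 reports "hypothyroidism in 8.3% (0.2 % Grade 3") among 411 melanoma patients given pembrolizumab. The side effects listed for blinatumomab in section 9.1 are "Cytokine release syndrome, hypotension, fever, respiratory distress, encephalopathy, confusion, seizure, infection, tumor lysis syndrome, neutropenia, febrile neutropenia, transaminitis". Hypothyroidism is not among them.

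**The concern.** The two rows take action on the drug for which the protocol does not list the event, and leave the drug for which it does. Blinatumomab is the approved, active leukemia therapy. Section 10.5.1 expects the response rate to PD-1 inhibitors in relapsed or refractory ALL to be close to zero. A site that follows the table would interrupt or end the active drug for an event that the same row treats with hormone replacement.

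The text offers no clear way out. Section 5.7 directs withholding according to the tables, and a relation to either drug is enough to trigger them. A site might spare blinatumomab because it attributes the event to pembrolizumab alone, but nothing says it may. Appendix G (section 1) refers dose-modification questions back to the protocol.

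At Grade 3 the footnote adds a second risk. If recovery to Grade 1 takes more than 14 days, the patient leaves protocol therapy altogether.

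**Working it through.** The documents state no figure on this point to reproduce. The check is a count over the tables, followed by a rough estimate of frequency and dose.

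**1. Tables.** Section 5.7.1 has 13: cytokine release syndrome (CRS), neurologic, infusion reactions, pneumonitis, diarrhea/colitis, nephritis, hypophysitis, hepatitis, type I diabetes, hyperthyroidism, hypothyroidism, other immune-mediated, and other non-hematologic. Section 5.7.2 has 2: neutropenia and thrombocytopenia. Total 15.

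**2. Rows that hold or stop blinatumomab.**

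| Source | Rows |
|---|---|
| CRS (Grades 3, 4) | 2 |
| Neurologic (Grades 3, 4; two seizure rows) | 4 |
| The other 11 tables in 5.7.1, two rows each (infusion reactions by reference to CRS) | 22 |
| Neutropenia Grade 4, thrombocytopenia Grade 4 | 2 |
| **Total** | **30** |

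Pembrolizumab is also held or stopped in 28 of the 30. The two exceptions are hypothyroidism Grade 3 and Grade 4. The nearest neighbour, hyperthyroidism, acts on both drugs at Grades 3 and 4.

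**3. Rows in the opposite direction.** Seven Grade 2 rows hold pembrolizumab and leave blinatumomab running: infusion reactions, pneumonitis, colitis, nephritis, hypophysitis, hepatitis and other immune-mediated. These follow the stated order.

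**4. Frequency of Grade 3.** Inputs: a rate of 0.2% (section 1.2.2) and 24 patients (section 10.2). Applying a melanoma monotherapy rate to this combination is an assumption.

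- Expected cases: 24 × 0.002 = 0.048.
- Chance of at least one: 1 − 0.998^24 = 0.047.

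This gives all 24 patients full exposure. Patients without CR/CRh after two cycles go off study (section 5.1.3), and on-treatment thyroid tests are scheduled only on Day 1 of Cycles 3 and 5. At response rates of 29% to 54% (section 10.5.1), 24 × 0.29 ≈ 7 to 24 × 0.54 ≈ 13 patients would reach Cycle 3:

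- 1 − 0.998^7 = 0.014.
- 1 − 0.998^13 = 0.026.

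Earlier clinical cases remain possible, so at this rate the range is about 1.4% to 4.7%.

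The source rate is itself imprecise. If 0.2% means 1 of 411, the exact 95% upper limit is 1.35%, and with all 24 exposed 1 − (1 − 0.01348)^24 = 0.278. No Grade 4 rate is cited, so none is computed.

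**5. Dose lost by an affected patient at Grade 3.** The 9 mcg/day restart costs up to 7 × (28 − 9) = 133 mcg, before counting held days.

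- Cycles 2–5: planned 28 × 28 = 784 mcg; 133/784 = 17%.
- Cycle 1: planned 7 × 9 + 21 × 28 = 651 mcg; 133/651 = 20%.

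**The case against.** The case for leaving the table alone has real substance.

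- **The order is advisory.** It asks that pembrolizumab adjustment be considered first. A sponsor could consider it, leave pembrolizumab unchanged, and comply literally. This stands: the rows depart from a stated preference and do not break a binding rule.
- **The pembrolizumab cell follows supplied guidance.** Appendix G, section 3.3, allows pembrolizumab to continue in Grade 2–4 hypothyroidism. This stands, and it points to the blinatumomab cells as the ones to correct. Pembrolizumab is not wholly untouched either, because a general rule in section 5.7.1 stops it when a Grade 3 event recurs.
- **The blinatumomab column follows a pattern.** The same hold, step-down restart and Grade 4 stop appear for nephritis, hypophysitis, diabetes and hyperthyroidism. The diabetes table is titled as an event developing on pembrolizumab, yet it acts on blinatumomab. A conservative blanket rule is therefore possible. It does not explain why these two rows alone spare pembrolizumab.
- **The event is rare.** This stands and limits the weight of the point.

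A reader might also infer that blinatumomab gets 14 days to recover while pembrolizumab has no limit, because endocrinopathies are exempt from the 12-week recovery rule for pembrolizumab. The documents do not support that contrast: on its wording, the 14-day footnote ends all protocol therapy, pembrolizumab included. The short window is also not special to hypothyroidism, since the hypophysitis, diabetes and hyperthyroidism tables share it.

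**Conclusion.** The point holds as an internal inconsistency in dosing instructions, confined to two rows. What the cells say, and that they are unique among the 30, is certain. That the blinatumomab cells are wrong is a judgement. It rests on the advisory order, on the event being listed under pembrolizumab only, and on Appendix G supporting the pembrolizumab cell. The documents do not show whether the cells were intended or copied from neighbouring tables.

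The effect is on individual patient care. At the cited rate the chance of one Grade 3 case in the trial is about 5% or less. The true rate with the combination is not given. A reader might infer a threat to the response-rate test, but nothing here changes the figures of the primary analysis.

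Two further inferences go beyond the text. One is that a Grade 4 patient will definitely continue on pembrolizumab alone. The table leaves that dose unchanged, but the footnote or the unacceptable-adverse-event criterion in section 5.8 may end treatment, so the outcome is unclear. The other is that the Grade 4 blinatumomab stop should be softened to a hold. Every other Grade 4 row in section 5.7.1 stops blinatumomab or ends protocol therapy. The stability wording in Appendix G that might seem to support a softer rule concerns resuming pembrolizumab after new-onset diabetes.

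**What to change.** **Grade 3.** Change the blinatumomab cell to an unchanged dose with thyroid replacement. This agrees with Appendix G on the pembrolizumab side and removes the route through the 14-day footnote. The drawback is that it becomes the only Grade 3 row in section 5.7.1 that holds neither drug. If the sponsor wants a hold, pembrolizumab should be held first.

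**Grade 4.** Do not stop blinatumomab while pembrolizumab continues unchanged. If the stop is kept, add one sentence saying that the patient is off protocol therapy and does not continue pembrolizumab alone.

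**If the present cells are intended,** say so in section 5.7.1 and give the reason.

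**Check before amending.** The DLT definition (sections 5.1.1 and 5.1.4) refers to these tables. Grade 3 or 4 laboratory abnormalities count when they warrant temporary discontinuation of pembrolizumab or permanent discontinuation of blinatumomab. Adding a pembrolizumab hold could therefore change how an event recorded as a laboratory abnormality is classified.

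**Cost.** One table cell and one sentence in an amendment, plus the DLT check. No extra assessments and no change to the sample size.

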5.7.2 Management of Hematologic Toxicities

Neutropenia	Management for Blinatumomab	Management for Pembrolizumab
General principles: Neutropenia management guidelines only apply if the patient is in complete bone marrow remission. If patient is not in complete remission in the bone marrow, then blinatumomab and pembrolizumab should be continued.		
≤ Grade 1	No change.	No change in dose
Grade 2	No change.	No change in dose
Grade 3	No change. Prophylactic antimicrobials may be given per institutional standard of care.	No change. Prophylactic antimicrobials may be given per institutional standard of care.
Grade 4	
If patient with documented bone marrow CR, then Withhold blinatumomab. Prophylactic antimicrobials may be given per institutional standard of care.
 
Restart blinatumomab at previous dose when toxicity improves to <Grade 2. Missed doses/days are not made up.
 
If patient in bone marrow CR and Grade 4 neutropenia persists for >28 days weeks despite withholding blinatumomab then permanently discontinue blinatumomab.
	
If patient with documented bone marrow CR, then Withhold pembrolizumab. Prophylactic antimicrobials may be given per institutional standard of care.
 
Restart pembrolizumab when toxicity improves to <Grade 2. Missed doses are not made up.
 
If patient in bone marrow CR and Grade 4 neutropenia persists for >28 days weeks despite withholding pembrolizumab then permanently discontinue pembrolizumab.

*Patients requiring a delay of blinatumomab >14 days due to toxicity should go off protocol therapy.		

Thrombocytopenia	Management for Blinatumomab	Management for Pembrolizumab
General principles: Thrombocytopenia management guidelines only apply if the patient is in complete bone marrow remission. If patient is not in complete remission in the bone marrow, then blinatumomab and pembrolizumab should be continued. Anti-platelet agents and anticoagulants should be used with caution in setting of thrombocytopenia.		
≤ Grade 1	No change.	No change.
Grade 2	No change.	No change.
Grade 3	No change.	No change.
Grade 4	
If patient with documented bone marrow CR, then withhold blinatumomab. Transfuse platelets as needed per institutional standard of care.
 
Restart blinatumomab at previous dose when toxicity improves to
	
If patient with documented bone marrow CR, then withhold pembrolizumab. Transfuse platelets as needed per institutional standard of care.
 
Restart pembrolizumab when toxicity improves to <Grade 2.

Thrombocytopenia	Management for Blinatumomab	Management for Pembrolizumab
	
<Grade 2. Missed doses/days are not made up.
 
If patient in bone marrow CR and Grade 4 toxicity persists for >28 days weeks despite withholding blinatumomab then permanently discontinue blinatumomab.
	
Missed doses are not made up.
 
If patient in bone marrow CR and Grade 4 toxicity persists for >28 days weeks despite withholding pembrolizumab then permanently discontinue pembrolizumab.

*Patients requiring a delay of blinatumomab >14 days due to toxicity should go off protocol therapy.
		

For toxicities not meeting Grade 3 or 4 toxicity but requiring cessation of either or both drugs treatment with offending drug(s) should be permanently discontinued.

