5.1.4 Stage I – Dose limiting toxicity definition and stopping rules

To determine the safety of pembrolizumab in combination with blinatumomab in patients with acute lymphoblastic leukemia, the combination will be administered to 3-6 patients with relapsed or refractory B-lineage acute lymphoblastic leukemia.

Toxicity will be graded according to the National Cancer Institute (NCI) Common Toxicity Criteria for Adverse Events (CTCAE) version 4.03. Adverse events will be assessed continuously throughout therapy.

Dose Limiting Toxicity (DLT) is defined as a clinically significant adverse event that is considered by the investigator to be probably or definitely related to pembrolizumab or the combination of pembrolizumab and blinatumomab occurring within 42 days of the first dose of pembrolizumab on Day 15 of Cycle 1 as follows:

- Any Grade 3-5 non-hematologic toxicity EXCEPT:
 - Grade 3 cytokine release syndrome that resolves in 7 days or less
 - Grade 3 neurotoxicity that resolves in 7 days or less
 - Grade 3 infections
 - Grade 3 or 4 febrile neutropenia unless deemed by investigator to be definitely related to pembrolizumab
 - Grade 3 or 4 laboratory abnormalities unless they warrant temporary discontinuation of pembrolizumab or permanent discontinuation of blinatumomab (see tables, 5.7.1 and 5.7.2)
 - Grade 3 or 4 lymphopenia
- Any clinically significant toxicity that precludes administration of the next scheduled dose for more than 14 days

Decision to proceed to Stage 2 of the study will be made as follows below.

Number of Patients with DLT	Decision Rule
0 out of 3	Proceed to Stage 2 of study.
1 out of 3	Enter at least 3 more patients. 
 If 0 of these 3 patients experience DLT, proceed to Stage 2 of study If 1 or more of this group suffer DLT, then study will be placed on hold. Decision regarding dosing of pembrolizumab and continuation of study will be made after discussion between sponsors and investigators.
≥ 2	Study will be placed on hold and the FDA notified. Decision regarding dosing of pembrolizumab and continuation of study will be made after discussion between sponsors, investigators and FDA.
≤ 1 out of 6	Proceed to Stage 2 of study.

Subjects withdrawing from investigational treatment during the DLT monitoring period for a reason that is definitely unrelated to toxicity of the study agent (e.g. disease progression, patient withdrawal of consent) will be replaced.

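### In both cytopenia tables of section 5.7.2, the 28-day limit in the Grade 4 cell and the 14-day limit in the footnote cannot both be followed for roughly days 15 to 28 of a blinatumomab hold

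*Combined protocol and SAP*

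**What the plan says.** Section 5.7.2 of the combined protocol and SAP has two tables, one for neutropenia and one for thrombocytopenia, each with a blinatumomab column and a pembrolizumab column.

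- **Scope.** The neutropenia table states: "Neutropenia management guidelines only apply if the patient is in complete bone marrow remission". The thrombocytopenia table has the same condition.
- **Grade 4 action for blinatumomab.** "If patient with documented bone marrow CR, then Withhold blinatumomab".
- **Restart.** "Restart blinatumomab at previous dose when toxicity improves to <Grade 2. Missed doses/days are not made up".
- **Time limit in the neutropenia cell.** "Grade 4 neutropenia persists for >28 days weeks despite withholding blinatumomab then permanently discontinue blinatumomab".
- **Time limit in the thrombocytopenia cell.** "Grade 4 toxicity persists for >28 days weeks despite withholding blinatumomab then permanently discontinue blinatumomab".
- **Footnote under each table.** "Patients requiring a delay of blinatumomab >14 days due to toxicity should go off protocol therapy".

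The pembrolizumab cells in both tables follow the same pattern of withholding, restarting below Grade 2, and stopping that drug after more than 28 days of persisting Grade 4.

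**The concern.** Each table sets two time limits for the same hold, and they do not agree. Under the cell, a patient in marrow remission whose Grade 4 cytopenia has lasted 20 days is still on hold and may restart. Under the footnote, the same patient left protocol therapy after day 14. The unit in the cell is also garbled, since days and weeks are printed together, so the sentence needs correcting in any case.

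At stake is consistent treatment across sites. Section 5.1.3 plans five cycles for patients with CR/CRh after two cycles, absent relapse. Which limit a site applies decides whether a patient with a prolonged cytopenia can resume treatment, how much of both drugs is given, and whether the patient counts as having completed the course. In a multicenter trial of 24 patients, a few discordant decisions would be visible in the exposure and tolerability summaries.

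**Working it through.** The plan gives no figure to reproduce. The check sets the rules side by side and counts days.

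**Inputs.** Cell limit: more than 28 days of persisting Grade 4 (5.7.2). Footnote limit: more than 14 days of blinatumomab delay (5.7.2). Cycle: 42 days, with infusion on days 1–28 (5.1.3), hence 42 − 28 = 14 planned infusion-free days.

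**Step 1: the rules side by side**

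| | Grade 4 cell | Footnote |
|---|---|---|
| Clock | persisting Grade 4 during a hold | delay of blinatumomab due to toxicity |
| Limit | more than 28 days | more than 14 days |
| Result | that drug permanently stopped | off protocol therapy |

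The results differ as well as the limits. The cytokine release and neurologic tables in 5.7.1 enter off protocol therapy in both drug columns for Grade 4 events, so the phrase covers pembrolizumab too. The cytopenia cells stop the two drugs separately.

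**Step 2: delay read as calendar days.** Up to day 14 both rules permit the hold. After day 28 of persisting Grade 4, both end blinatumomab. From day 15 to day 28, which is 28 − 14 = 14 days, the cell keeps the patient eligible to restart and the footnote does not.

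**Step 3: delay read as missed infusion days only.** This reading favors the plan most. For a hold of H days starting on cycle day s, with the 42-day calendar running on into a next cycle, days lost = the number of d from s to s + H − 1 with ((d − 1) mod 42) + 1 ≤ 28.

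For H = 28:
- s = 1: days 1–28, 28 lost.
- s = 14: days 14–28, 15 lost.
- s = 15: days 15–28, 14 lost.
- s = 29: rest days 29–42, then next-cycle days 1–14, 14 lost.
- s = 30: rest days 30–42, then next-cycle days 1–15, 15 lost.

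| Hold (days) | Infusion days lost, min–max | Start days losing more than 14 (of 42) | Same, infusion-day starts only (of 28) |
|---|---|---|---|
| 14 | 0–14 | 0 | 0 |
| 15 | 1–15 | 14 | 14 |
| 21 | 7–21 | 20 | 14 |
| 28 | 14–28 | 27 | 14 |
| 29 | 15–28 | 42 | 28 |

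A 28-day hold therefore breaches the footnote for starts on days 1–14 and 30–42 (14 + 13 = 27 of 42). It loses exactly 14 days for the other 15 starts (days 15–29), where both rules can be met. If only holds that begin on an infusion day are counted, the footnote is breached for 14 of 28.

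**Step 4: two clocks inside the cell.** The 28-day limit counts persisting Grade 4, but restart needs less than Grade 2. A patient who improves to Grade 2 or 3 can neither restart nor reach the 28-day limit. For that patient the footnote is the only stated time limit, if it applies.

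**Step 5: precedence.** Section 5.7 directs sites to the system with the greatest toxicity, but it does not rank time limits. No other text does so for these rows.

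**The case against.** The strongest defense is that the footnote does not govern these rows. It is a marked note. Most tables in 5.7.1 attach the asterisk to the instruction to withhold, and no cytopenia cell carries one. The specific Grade 4 rule could then prevail over carried-over general text. This is plausible but does not settle the matter. The note is printed under both cytopenia tables in unconditional wording, and anchoring is not reliable elsewhere: the infusion-reaction table prints the same note with no asterisk in any cell, although its blinatumomab cells do refer back to the cytokine release table.

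The second defense is that delay is undefined and may mean missed infusion days. This stands in part: for 15 of 42 start days a 28-day hold satisfies both rules. A reader might infer that the 28-day limit can never be reached, and on this reading that is not so.

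Other stronger readings also fail:

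- **That the rules are opposite.** Both eventually stop treatment. They conflict within a window.
- **That every responder is exposed, about 7 of 24 at the null rate (0.29 × 24 = 6.96) or 13 of 24 at the target (0.54 × 24 = 12.96).** These are expected CR/CRh counts. The tables apply to marrow remission, whereas CR and CRh in 7.1.4.1 also need count recovery. Section 5.7 limits dose changes to toxicity at least possibly related to study drug. No incidence of prolonged Grade 4 cytopenia is given.
- **That follow-up for relapse-free survival changes.** Section 5.9 continues relapse and survival follow-up after removal for adverse events.
- **That the DLT criterion must match.** Section 5.1.4 counts "Any clinically significant toxicity that precludes administration of the next scheduled dose for more than 14 days". Whether that is met does not depend on which discontinuation limit applies, and the two serve different purposes.

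**Conclusion.** The inconsistency is real and appears in both tables. As written, the stopping rule for Grade 4 cytopenia in marrow remission cannot be followed for days 15 to 28 of a hold on the calendar reading. On the missed-infusion-day reading, a 28-day hold conflicts for 27 of 42 start days, or 14 of 28 if the hold begins on an infusion day. Those counts assume a fixed 42-day calendar with a following cycle, so they do not describe a hold that runs past the end of cycle 5.

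The consequence is possible site-to-site variation in exposure to both drugs and in completion of the five planned cycles. The number of patients affected cannot be estimated from the documents. No alpha, power or sample-size figure changes. This point does not say which limit is right.

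**What to change.** In both tables of section 5.7.2 the sponsor should:

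1. Reconcile the more-than-28-day cells with the more-than-14-day footnote, so that one instruction applies at each point of a hold.
2. State whether the footnote applies to the Grade 4 cytopenia rows and whether it also ends pembrolizumab, given that drug's own 28-day limit.
3. Define delay as calendar days or missed infusion days. The last table in 5.7.1 measures delay of the next cycle instead, so the term is not used uniformly.
4. Correct the doubled unit in all four Grade 4 cells.

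The choice of limit is the sponsor's clinical decision, and the DLT criterion need not be changed to match. The cost is an amendment to wording, with no added procedures or patients.
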